Specific test results will not be released, since they are assessing immune response over time to determine the effect of the treatment on the immune response. Overall study results can be shared with the patients.

Please identify all third parties, including the subject's physician, to receive the test results.

None

SAMPLE: Other 1: Tumor cytobrushing

What is the purpose of the sample collection?

Two sterile disposable cytobrushes (Cytobrush Plus GT (Cooper Surgical, Trumbull, CT)) will be used to collect cells from the cervix by rotating the brush 360 with 3 to 4 full rotations against the tumor. Study of specific immune markers and modalities by which the combination immunotherapy boosts the immune system and works in sync with the standard of care to enhance its effects. Immune biomarker assays will be taken at the beginning, middle, and end of the treatment to measure using flow cytometry.

For blood draws, specify the amount drawn, in teaspoons, at each visit and across the course of the subjects entire participation time.

N/A

Is there the possibility that cell lines will be developed with this sample? No

Sample will be obtained from:

Other: Provider

Will the sample be stripped of identifiers?

No

If sample will be released outside the hospital:

Will sample be released to anyone not listed as an investigator on the protocol? Will the information be identifiable, coded or de-identified?

No

Will sample material be sold or transferred to any third parties? Will the information be de-identified?

No

If sample will be banked for future use:

Where will the sample be banked and for how long?

Sample will not be banked

Does the banking institution have an approved policy for the distribution of samples?

N/A

If the entire sample will NOT be used during the course of this research study:

Will the remaining tissue be discarded? If not what will be done with the remaining sample after study completion and how long will the sample be kept?

Remaining tissue will be stored in our -80 freezer located in our laboratory. Samples will be stored with a study ID and all patient identifiers will be removed. All samples will be disposed upon study publication.

Will samples be made available to the research subject (or his/her medical doctor) for other testing?

No

If a subject withdraws from the study:

Will subject have the option to get the remaining portion of their sample back?

No

Will samples be destroyed? If not, will they be kept anonymously? What will happen to the sample if the subject revokes authorization?

yes

Will data obtained from their sample be deleted? What will happen to the sample if the subject revokes authorization?

Data collected from samples will be password protected and stored on the BCM secure serve. If a subject revokes authorization their data will be deleted.

Will study data or test results be recorded in the subject's medical records?

No

Will results of specific tests and/or results of the overall study be revealed to the research subject and or his/her doctor?

Specific test results will not be released, since they are assessing immune response over time to determine the effect of the treatment on the immune response. Overall study results can be shared with the patients.

Please identify all third parties, including the subject's physician, to receive the test results.

N/A

SAMPLE: Tissue

What is the purpose of the sample collection?

Baseline evaluation of immunity prior to initiation of treatment

For blood draws, specify the amount drawn, in teaspoons, at each visit and across the course of the subjects entire participation time.

N/A

Is there the possibility that cell lines will be developed with this sample? No

Sample will be obtained from:

Pathology

Will the sample be stripped of identifiers?

No

If sample will be released outside the hospital:

Will sample be released to anyone not listed as an investigator on the protocol? Will the information be identifiable, coded or de-identified?

No

Will sample material be sold or transferred to any third parties? Will the information be de-identified?

No

If sample will be banked for future use:

Where will the sample be banked and for how long?

No

Does the banking institution have an approved policy for the distribution of samples?

N/A

If the entire sample will NOT be used during the course of this research study:

Will the remaining tissue be discarded? If not what will be done with the remaining sample after study completion and how long will the sample be kept?

Stored in pathology

Will samples be made available to the research subject (or his/her medical doctor) for other testing?

No

If a subject withdraws from the study:

Will subject have the option to get the remaining portion of their sample back?

No

Will samples be destroyed? If not, will they be kept anonymously? What will happen to the sample if the subject revokes authorization?

yes

Will data obtained from their sample be deleted? What will happen to the sample if the subject revokes authorization?

yes

Will study data or test results be recorded in the subject's medical records?

No

Will results of specific tests and/or results of the overall study be revealed to the research subject and or his/her doctor?

Results of the overall study will be shared with the subject

Please identify all third parties, including the subject's physician, to receive the test results.

N/A

Section O: Drug Studies

Does the research involve the use of ANY drug* or biologic? (*A drug is defined as any substance that is used to elicit a pharmacologic or physiologic response whether it is for treatment or diagnostic purposes)

Yes

Does the research involve the use of ANY gene transfer agent for human gene transfer research?

No

O1. Current Drugs

Drug : Human Papillomavirus 9-valent Vaccine, Recombinant (Gardasil9)

Drug : imiquimod 5% cream (Aldara)

Drug : metformin

Is this study placebo-controlled?

No

Will the research involve a radioactive drug?

No

Section P: Device Studies

Does this research study involve the use of ANY device?

No

Section Q: Consent Form(s)

HPV 9-valent vaccine, recombinant; imiquimod; and metformin (HPV VIM) Trial

Section R: Advertisements

None

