
Section D: Purpose and Objectives

PRIMARY: The primary objective of the study is to determine the effect on 24 month progression free survival of intratumoral HPV vaccination with topical imiquimod and oral metformin for locally advanced cervical, vaginal, or vulvar carcinoma in conjunction with definitive whole pelvic radiotherapy with chemotherapy followed by brachytherapy. Although the clinical benefit of this combination of drugs has not yet been established, the intent of offering this treatment is to provide a possible therapeutic benefit, and thus the patient will be carefully monitored for tumor response and symptom relief in addition to safety and tolerability.

SECONDARY: Assess for unanticipated toxicity of the combination of intratumoral HPV vaccination with topical imiquimod and oral metformin when administered in conjunction with chemotherapy with whole pelvic radiotherapy for cervical or vulvar carcinoma. .

Corollary Objective: Study of specific immune markers and modalities by which the combination immunotherapy boosts the immune system and works in sync with the standard of care to enhance its effects. Immune biomarker assays will be performed in cervical swab and blood samples at the beginning, middle, and end of the treatment to measure the effects of treatment on several immune markers including: CD4, CD8, NK, TNF alpha and beta, IL2, HPV viral load, TGF Beta, Ki67, IgG. We will also do blood tests to test for IgG L1 and L2, E6 and E7 and a CBC. These markers were chosen to identify specific immune changes of the three treatment groups.

Section E: Protocol Risks/Subjects

E1. Risk Category

Category 2: Research involving greater than minimal risk, but presenting the prospect of direct benefit to the individual subjects.

E2. Subjects

Gender:

Female

Age:

Adult (18-64 yrs)

Ethnicity:

All Ethnicities

Primary Language:

English, Spanish

Groups to be recruited will include:

Asymptomatic patients with chronic conditions, healthy; Patients

Which if any of the following vulnerable populations will be recruited as subjects?

Vulnerable populations require special protections. How will you obtain informed consent, protect subject confidentiality, and prevent undue coercion?

E3. Pregnant woman/fetus

Will pregnant women and/or fetuses (as described in 45 CFR 46 Subpart B) be enrolled in the research?

No

E4. Neonates

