Will neonates of uncertain viability or nonviable neonates (as described in 45 CFR 46 Subpart B) be enrolled in the research?

No

E5. Children

Will children be enrolled in the research?

No

Section F: Design/Procedure

F1. Design

Select one category that most adequately describes your research:

u) Drug, Phase II, Single Center

Discuss the research design including but not limited to such issues as: probability of group assignment, potential for subject to be randomized to placebo group, use of control subjects, etc.

This window-of-opportunity study will be offered to all eligible patients undergoing chemoradiation for cervical, vulvar, or vaginal cancer, since it is an additional treatment anticipated to enhance the response to therapy. The treatment group will be compared to a historical control. We will evaluate the immune changes within the tumor microenvironment and validate why the combination immunotherapy study elicited such a robust immune response which led to complete resolution of the cancer, in comparison to the standard of care, chemoradiation. If the combination immunotherapy used together with chemoradiation elicits a more robust antitumor response, there is the potential that the addition of these FDA approved medications to chemoradiation could be a new standard of treatment for squamous cell carcinoma of the cervix and vulva.

Inclusion Criteria:

- Participants must have histologically confirmed locally advanced or metastatic cervical carcinoma (Stage IB2-IVB), vaginal, or vulvar carcinoma (Stage II-IVB), AND not be considered a primary surgical candidate. Patients offered neoadjuvant therapy may be enrolled if they respond and receive chemoradiation. • Participants must have measurable disease, per Recist criteria. See Section 12 (Measurement of Effect) for the evaluation of measurable disease.
- Radiological evaluation shall occur within approximately 30 days prior to enrollment initiation and start of radiation.
- Participants must have an Eastern Cooperative Oncology Group (ECOG) performance status of ≤ 2
- Participants must be ≥ 18 years of age

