(EBRT) and brachytherapy is permitted for cervical or vaginal carcinoma, and chemoradiation with EBRT for vulvar carcinoma. A lesion must be readily accessible for intratumoral tumor injection. • ECOG performance status ≤2 (Karnofsky ≥60%, see Appendix A). • For patients with evidence of chronic hepatitis B virus (HBV) infection, the HBV viral load must be undetectable on suppressive therapy, if indicated. • Patients with a history of hepatitis C virus (HCV) infection must have been treated and cured. For patients with HCV infection who are currently on treatment, they are eligible if they have an undetectable HCV viral load. • Patients with treated brain metastases are eligible if follow-up brain imaging after central nervous system (CNS)-directed therapy shows no evidence of progression. • Patients with a prior or concurrent malignancy whose natural history or treatment does not have the potential to interfere with the safety or efficacy assessment of the investigational regimen are eligible for this trial.

Exclusion Criteria:

- Patients who are receiving any other investigational agents.
- Patients who have untreated, new or progressive brain metastases or leptomeningeal disease.
- History of allergic reactions attributed to compounds of similar chemical or biologic composition to agents used in study.
- Patients with uncontrolled intercurrent illness.
- Patients with psychiatric illness/social situations that would limit compliance with study requirements.
- Pregnant women are excluded from this study because cervical carcinoma or vulva carcinoma patients have undergone treatment rendering the patient infertile. Because there is an unknown but potential risk for adverse events in nursing infants secondary to treatment of the mother with cervical carcinoma or vulva carcinoma, breastfeeding should be discontinued.

F2. Procedure

Treatment visits will occur during the second and fourth weeks of radiation, and then during weeks 8, 10, 12, and 16, which will occur after completing radiation.

At the treatment visit:

A blood sample will be obtained by a research nurse (10 milliliters/ 2 teaspoons)

A speculum exam will be performed and 2 small brushes (cytobrush) will be used to collect cells from the surface of the tumor. If you have a vulvar cancer, the cells will be collected from the tumor surface.

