HPV 9-valent recombinant vaccine (3 milliliters/approximately ½ teaspoon) will be injected into several locations on the tumor surface, using ½ half of the single dose vaccine diluted with saline solution.

If you have cancer of the vulva, the vaccine will be injected without placing the speculum.

Imiquimod cream will be applied to the surface of the tumor at the visit.

You will then receive ½ of the vaccine dose as a subcutaneous shot.

Following the visit, you will receive 6 small doses of imiquimod cream in individual packets. These are to be applied using a vaginal applicator 3 nights per week for the next 2 weeks.

If you have cancer of the vulva, the imiquimod cream will be applied directly on the tumor surface.

You will also receive metformin 500 mg tablets, which are to be taken by mouth twice daily for the next 2 weeks.

A PET/CT test will be performed at treatment completion (week 20), then PET/CT or CT chest/abdomen/pelvis 2 years post treatment. You will have follow-up visits with a physical exam including pelvic exam every 3 months up until 2 years.

Section G: Sample Size/Data Analysis

G1. Sample Size

How many subjects (or specimens, or charts) will be used in this study?

Local: 85 Worldwide: 85

Please indicate why you chose the sample size proposed:

The planned cohort size will be 77 primary cervical cancer patients, the number needed for the evaluation of improvement in time to progression-free survival, with up to 8 vulvar/vaginal cancer patients, since they are rare. Members of the protocol study team have completed a comprehensive review of local control outcomes for all women treated for a locoregionally advanced cervical cancer (bulky FIGO IB3- IVA) with chemoradiotherapy to include standard of care concurrent cisplatin at the Harris Health System. Twenty-four month progression-free survival for patients who presented with FIGO IIIA-IVA cervical cancer is 67%. Since this clinical trial is enrolling an advanced stage cohort, we estimate that PFS would be 67% with standard of care and we will consider the trial a success if PFS is better than 77% at 24 months. Employing a one-sample exponential hazard rate test, and using a survival time of at least 2 years, which is consistent with the follow up time of 2 years, a sample of 77 patients are needed (alpha=10%, one-tailed, history control PFS24 m=67% vs new PDA24m=77%). Similar results are obtained for a standard one-sample log-rank test. .

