What is the purpose of the sample collection?

Evaluate immune response

For blood draws, specify the amount drawn, in teaspoons, at each visit and across the course of the subjects entire participation time.

10 mL (2 teaspoons) blood in EDTA-coated tubes at each of the 3 treatment visits (prior to initial treatment, mid treatment, and 6 months post treatment initiation). Peripheral blood samples will be collected in EDTA-coated tubes and peripheral blood mononuclear cells (PBMCs) will be isolated from the blood using the standard procedure with LymphoprepTM (Stemcell technologies, Cambridge, MA) density gradient centrifugation for use in flow cytometry analysis.

Is there the possibility that cell lines will be developed with this sample? No

Sample will be obtained from:

Clinical Labs

Will the sample be stripped of identifiers?

No

If sample will be released outside the hospital:

Will sample be released to anyone not listed as an investigator on the protocol? Will the information be identifiable, coded or de-identified?

N/A

Will sample material be sold or transferred to any third parties? Will the information be de-identified?

N/A

If sample will be banked for future use:

Where will the sample be banked and for how long?

N/A

Does the banking institution have an approved policy for the distribution of samples?

N/A

If the entire sample will NOT be used during the course of this research study:

Will the remaining tissue be discarded? If not what will be done with the remaining sample after study completion and how long will the sample be kept?

Yes

Will samples be made available to the research subject (or his/her medical doctor) for other testing?

No

If a subject withdraws from the study:

Will subject have the option to get the remaining portion of their sample back?

No

Will samples be destroyed? If not, will they be kept anonymously? What will happen to the sample if the subject revokes authorization?

Yes

Will data obtained from their sample be deleted? What will happen to the sample if the subject revokes authorization?

Data collected from samples will be password protected and stored on the BCM secure serve. If a subject revokes authorization their data will be deleted.

Will study data or test results be recorded in the subject's medical records?

No

Will results of specific tests and/or results of the overall study be revealed to the research subject and or his/her doctor?

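### The immune objective implies a comparison with standard chemoradiation and several treatment groups, but the trial has one arm, no chemoradiation-only samples and conflicting sampling schedules

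*Protocol*

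**What the plan says.** **Design.** F1 describes one treated group without allocation: "This window-of-opportunity study will be offered to all eligible patients undergoing chemoradiation for cervical, vulvar, or vaginal cancer". The comparator is external: "The treatment group will be compared to a historical control". Section G1 describes that comparator as clinical data; the study team members "have completed a comprehensive review of local control outcomes for all women treated for a locoregionally advanced cervical cancer", from which a 24-month PFS of 67% is taken.

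**Immune aim.** F1 states: "We will evaluate the immune changes within the tumor microenvironment and validate why the combination immunotherapy study elicited such a robust immune response". The same sentence ends by setting this "in comparison to the standard of care, chemoradiation". The corollary objective in Section D lists the markers (CD4, CD8, NK, cytokines, HPV viral load, Ki67, IgG, and IgG to L1, L2, E6 and E7) and adds: "These markers were chosen to identify specific immune changes of the three treatment groups".

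**Sampling.** F2 places blood and cytobrush collection at the treatment visits: "Treatment visits will occur during the second and fourth weeks of radiation", then weeks 8, 10, 12 and 16. H1 gives three blood time points, the first before treatment and the last six months after it. Section N also gives three, calls them treatment visits, places the first "prior to initial treatment" and counts the last six months from the start of treatment. Section N adds pathology tissue as a pre-treatment immune baseline.

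**The concern.** A comparison with standard care needs immune data from patients who received standard care alone. If none exist, a change in a marker during the trial shows what happened under chemoradiation plus vaccine, imiquimod and metformin together. Chemoradiation can itself move cell counts, proliferation markers and viral load, so a reader could credit the study drugs with changes that radiation and cisplatin produced.

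The sampling conflict adds to this. If the first sample is taken in week 2 of radiation, the state before chemoradiation is not recorded in blood or cytobrush, and it cannot be recovered afterwards. Neither problem can be left to the analysis plan, because no analysis can supply control samples or a missed baseline.

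**Working it through.** No arithmetic in the plan bears on this point, so the check sets the sections side by side.

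**1. Groups with immune samples.** Section D names three; F1 provides one. Two readings of the three groups are possible:
- Three drugs: every patient receives all three, so they define no groups.
- Three tumor sites: all sites receive the same study drugs. G1 plans 77 cervical patients and up to 8 vulvar or vaginal patients together (77 + 8 = 85), and says the latter are too few for statistical comparison.

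Neither reading yields a chemoradiation-only group. Samples described from such patients: 0.

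**2. What one arm can identify.** For a marker at time t, write the change from a pre-radiation baseline as

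Δ(t) = C(t) + D(t),

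where C is the change chemoradiation would cause alone and D is what the study drugs add, including any interaction. Only Δ(t) is observed: one quantity, two unknowns. A chemoradiation-only group would estimate C(t). Without it:
- From pre-radiation to a week-2 sample taken before the first study-drug dose, D = 0, so Δ(2) = C(2). This shows the early chemoradiation change only.
- From week 2 onward, Δ(t) − Δ(2) = [C(t) − C(2)] + D(t). Chemoradiation continues past week 2, so the first term is not zero in general and the sum cannot be split.

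For IgG against L1, the protein that Section C links to the vaccine, it is reasonable to assume that chemoradiation alone would not raise the level. A rise would then point to D. That is an assumption about one marker and does not carry over to CD4, CD8, NK, Ki67 or viral load.

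**3. Sampling schedule.**

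| Place | Sample | Occasions | First | Last |
|---|---|---|---|---|
| D | blood, swab | 3 | start of treatment | end of treatment |
| F2 | blood, cytobrush | 6 | week 2 of radiation | week 16 |
| H1 | blood | 3 | before treatment | 6 months after treatment |
| N, blood | blood | 3 | before initial treatment | 6 months after treatment start |
| N, cytobrush | cytobrush | 3 | start of treatment | end of treatment |
| N, tissue | pathology tissue | 1 | before treatment | no later tissue described |

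The count differs (6 against 3), and so do both ends. Assume that F2 numbers weeks from the start of radiation and that six months is 26 weeks. The last sample then falls at week 16 under F2. Under Section N it falls at week 28 if treatment start means the first study-drug dose (2 + 26). Under H1 it falls at week 42 if counted from the last treatment visit (16 + 26). The word treatment is not tied to chemoradiation or to the study drugs in any of these places.

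**4. Baseline.** Under F2 the first sample follows at least one week of radiation. Under H1 it may precede radiation. Section N can be read either way, because it places the draw before initial treatment and also calls it a treatment visit. The pathology tissue is clearly pre-treatment but has no later tissue to pair with.

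**The case against.** - **The F1 sentence may be loose background.** It is in the past tense and speaks of a response already seen, which fits the case reports mentioned in Section J2. Section D's objective asks how the combination works together with standard care and states no between-group test. This has some force, but the sentence says what the trial will evaluate, and Section D still gives treatment groups as the reason for choosing the markers. Both need correction.
- **A pre-radiation baseline may already be intended.** H1 and Section N put the first draw before treatment, and J2 has patients approached in the weeks before radiation. This stands. A reader of F2 might infer that every baseline is taken after chemoradiation has started; the documents do not support that as a fact, only as what follows from F2.
- **A week-2 sample is not spoiled for the study drugs.** F2 lists blood and cytobrush ahead of injection and imiquimod, and metformin is handed out for the following two weeks. If the listed order is kept, that sample precedes all three. This also stands, and it is a reason to keep the sample.
- **Markers differ.** Anti-L1 IgG is more attributable to the vaccine than the rest, and four of the six visits fall after radiation. The first part stands. The second does not remove the problem, since effects of chemoradiation can persist after it ends.
- **The objective is corollary.** It carries no alpha, sample size or decision rule. This limits the importance of the point but does not make the objective answerable.

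**Conclusion.** The immune objective does not match the design. One group has immune samples against three named, and no chemoradiation-only samples are described, so the F1 comparison cannot be delivered. For most listed markers the study-drug effect cannot be separated from the chemoradiation effect; anti-L1 IgG is a partial exception, on the assumption stated above. Separately, the sampling passages contradict one another on the number of draws, the first draw and the last.

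Three stronger conclusions might be drawn and are not supported. The documents do not establish that the baseline is always taken during radiation. They do not make every marker uninterpretable. They also do not show that chemoradiation changes will be reported as drug effects, since no marker analysis is given here. The primary PFS comparison is not affected.

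The conclusion rests on no chemoradiation-only immune samples being collected under some other document. It does not depend on how the baseline conflict is resolved: with a true pre-radiation baseline, later change would still be a sum of the two effects.

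**What to change.** **Wording (D and F1).** Delete the reference to three treatment groups and the immune comparison with standard chemoradiation. State the objective as descriptive within-patient change under the combined regimen.

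**Schedule (D, F2, H1 and N).** Replace the separate descriptions with one research-sampling schedule that:
- takes baseline blood and cytobrush before the first radiation fraction;
- keeps the F2 week-2 sample, explicitly taken before the first study-drug dose, as the pre-vaccine value;
- says which later treatment visits include samples, and from which event the six-month draw is counted;
- states that the change from baseline to week 2 reflects chemoradiation alone, and that later change reflects chemoradiation and study drugs together.

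**Cost.** The mechanistic claim becomes weaker. Baseline, week 2, mid-treatment and six months make four draws against three in H1 and N, which is 10 mL more blood (40 mL against 30 mL), and H1's statement that no added draws are needed would have to change. Doses, eligibility and the primary test stay as they are. If the sponsor wants to keep the comparison with standard care, it would have to collect the same samples from patients on chemoradiation alone, a cohort that the protocol does not now contain.

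### The 67% benchmark is not stated to share the trial's response-conditional entry, its open checkpoint-inhibitor use or its stage range, so a difference from 67% cannot be credited to the study drugs alone

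*Protocol*

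**What the plan says.** Section F1 declares the control: "The treatment group will be compared to a historical control". Section G1 gives its source, a local review that took in "all women treated for a locoregionally advanced cervical cancer (bulky FIGO IB3- IVA"). The treatment those women received is described there as care "with chemoradiotherapy to include standard of care concurrent cisplatin at the Harris Health System". From this review comes the null: "Twenty-four month progression-free survival for patients who presented with FIGO IIIA-IVA cervical cancer is 67"%. G1 carries this figure over because the trial enrols an advanced-stage cohort, and gives no other reason. It then states that "we will consider the trial a success if PFS is better than 77% at 24 months". The test is one-sided at 10%, with 77 cervical patients. G2 compares 24-month PFS with a historical cohort by Kaplan-Meier and log-rank.

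The F1 criteria admit "histologically confirmed locally advanced or metastatic cervical carcinoma (Stage IB2-IVB"). On earlier treatment they say "Patients offered neoadjuvant therapy may be enrolled if they respond and receive chemoradiation". The only exclusion that concerns other anticancer drugs is "Patients who are receiving any other investigational agents".

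Section C describes immunotherapy as a recent addition for PD-L1-positive advanced disease. Sections C and I both say that vulvar and vaginal cancers typically receive chemoradiation, with pembrolizumab when PD-L1 positive, and liken this to the handling of squamous cervical cancer.

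**The concern.** With one arm and a fixed comparator, everything depends on 67% being what these patients would achieve without the study drugs. Stage is the only ground offered for that. Three features of the trial population are left unaddressed:

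- Patients who had neoadjuvant therapy enter only after a favourable early outcome.
- Approved checkpoint inhibitors may be given alongside, and the protocol's own background treats them as part of current practice.
- The eligible stages extend beyond IIIA-IVA at both ends.

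If standard-care PFS under these rules is not 67%, the primary test measures that gap together with any drug effect and cannot separate the two. F1 says a more robust response could make the regimen a new standard of treatment, so attribution matters here.

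**Working it through.** **Stated sample size.** Inputs from G1: null 67%, alternative 77%, one-sided alpha 10%. Under exponential PFS the hazard ratio is ln(0.77)/ln(0.67) = 0.653. Power and accrual time are not given, so 77 cannot be reproduced from stated inputs alone. It is reachable. With 80% power, events = (1.282 + 0.842)² / ln(0.653)² = 24.75. With 2 years of uniform accrual plus 2 years of follow-up, the event probability under the alternative is about 0.322, and 24.75/0.322 ≈ 77. The 77 is not disputed here.

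**Comparability of trial and benchmark.**

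| Feature | Trial (F1) | Source of the 67% (G1) |
|---|---|---|
| Stage | IB2-IVB | IIIA-IVA, within a review of IB3-IVA |
| Neoadjuvant therapy | admitted if the patient responds | not mentioned |
| Checkpoint inhibitor | not restricted | not mentioned; cisplatin chemoradiotherapy |

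**Illustration of size.** The shares and subgroup PFS values are assumptions; the documents give none. Model: exponential PFS, every patient followed for 24 months, study drugs inactive, one-sample log-rank test against 67% at one-sided 10%, by simulation. When all 77 are at 67% the test rejects in 9.3% of trials; its power at a true 77% is 74%. With 8, 15 or 23 of the 77 (10%, 20%, 30%) at a different 24-month PFS and the rest at 67%, it rejects as follows:

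| Subgroup PFS | 8 of 77 | 15 of 77 | 23 of 77 |
|---|---|---|---|
| 60% | 7% | 6% | 4% |
| 72% | 11% | 13% | 15% |
| 77% | 13% | 17% | 22% |
| 80% | 14% | 20% | 27% |
| 85% | 16% | 25% | 38% |

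A simple check: 30% of patients at 77% gives an average of 0.7 × 67 + 0.3 × 77 = 70%. The normal approximation for a true null of 70% also gives 22%.

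**Stage can push either way.** With 15 patients at 77% and 8 stage IVB patients at 40%, 50% or 60%, rejection is about 6%, 10% or 14%, so the inflation can vanish. If IB2-IIB patients do better than 67%, they shift the average upward in the same way as the subgroup in the table. Setting all remaining patients at 67% is therefore itself an assumption.

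**The other reading of success.** If success means an observed proportion above 77%, at least 60 of 77 must be progression-free (60/77 = 77.9%; 59/77 = 76.6%). The exact probability with inactive drugs is 2.5% at the reference. With 8, 15 or 23 patients at 77% it is 3.8%, 5.3% or 7.8%. In the scenarios above it exceeds 10% only with 23 patients at 80% (10.5%) or at 85% (16.4%).

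**The case against.** The strongest reply is that this is the ordinary limit of a single-arm phase II trial with an openly declared historical control, and that silence about the review is not a demonstrated mismatch. Much of that is fair:

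- The review covers all women treated with chemoradiotherapy, so it may already contain neoadjuvant responders. Reaching chemoradiation is a condition in both groups.
- The measurable-disease and accessible-lesion criteria in F1, read at enrolment, limit entry of complete responders, which bounds the selection.
- G2 speaks of a historical cohort, which could mean patient-level data and an adjusted comparison, with the detail left to the SAP.
- Every figure for size above is assumed, and under the observed-PFS reading the false-success rates are mild.

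What stands is that the null, the entry rules and the success threshold are all fixed in the protocol, and the only stated bridge between them is stage, which does not match either. The team holds the charts that could settle part of the question.

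A reader might infer that the 67% is too low and a false positive is therefore likely. The documents do not support that. Responders may have begun with worse disease, stage IVB may pull the other way, and no shares are given. A reader might equally infer that checkpoint inhibitors will be routine among the 77. The background makes some use plausible but gives no share for locally advanced cervical cancer.

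**Conclusion.** The point holds as one of attribution, not of a known bias. The 67% is not stated to reflect response-conditional entry, checkpoint-inhibitor co-treatment or the trial's stage range, so a result above or below it cannot be ascribed to the study drugs alone. Neither direction nor size can be established from the protocol. Over the assumed subgroup scenarios, the false-positive rate of the nominal 10% log-rank test runs from 4% to 38%, against 9% at the reference. The moderate case of a subgroup at 77% gives 13% to 22%. These figures rest on exponential PFS, complete 24-month follow-up and the remaining patients being at 67%. The remedy is cheap and improves the trial's main efficacy comparison, so it should be made, but the design is not invalidated.

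**What to change.** 1. In the existing chart review, count how many of the 67% cohort had neoadjuvant therapy or a checkpoint inhibitor. Re-derive the null for the trial's entry rules and stage mix as far as the review allows; it covers IB3-IVA. State the resulting figure, and restate null and target together if it moves. State that stage IVB cannot be matched, nor checkpoint-inhibitor co-treatment if the review contains none.
2. Record neoadjuvant therapy and planned checkpoint-inhibitor use for every patient at enrolment.
3. Prespecify a sensitivity analysis, not a second success gate, that repeats the one-sided 10% test without those patients. Report both 24-month PFS estimates with intervals, and limit attribution to the study drugs if the results disagree.

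Eligibility and the 77 stay unchanged, and the primary test loses no power through the sensitivity analysis.

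The cost is some chart work, two data fields and a paragraph of text. The subset analysis is less precise: with 69, 62 or 54 patients left, its power at a true 77% is about 70%, 67% or 62-63%, against 74% for all 77. The 95% half-width, 1.96 × √(0.77 × 0.23/n), is 9.9, 10.5 or 11.2 points, against 9.4. If the regimen works equally in everyone (all at 77%), the subset test still fails by chance in about 9%, 15% or 21% of trials that pass the primary test, which is why disagreement should temper the claim and not overturn the result.

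If the null moves to 65%, 69% or 72% while the true value stays at 77%, 77 patients give 85%, 60% or 37% power. If the 10-point gain is kept, power is 73%, 75% or 78%.
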